7.3 Assessment of Adverse Events

7.3.1 Severity

The Investigator should assess the severity of each AE. The AE will be recorded at its initial severity level. The initial AE will be considered ended and a new AE will be recorded if the event changes in severity.

The severity of all AEs, both serious and non-serious, will be assessed by assigning a grade of 1, 2, 3, 4, or 5 according to the latest version of Common Terminology Criteria for Adverse Events (CTCAE).

When an AE cannot be graded by CTCAE, the following severity grading may be used:

- Grade 1 (Mild): awareness of sign or symptom, but easily tolerated
 - Grade 2 (Moderate): discomfort enough to cause interference with usual activity
-

- Grade 3 (Severe): incapacitating with inability to work or do usual activity
- Grade 4 (Life-Threatening): refers to an event in which the patient was, in the view of the Investigator, at risk of death at the time of the event. (This category is not to be used for an event that hypothetically might have caused death if it were more severe.)
- Grade 5 (Fatal): death related to AE

An AE that is assessed as severe should not be confused with an SAE. Severity is a category for rating the intensity of an event, and both non-serious AEs and SAEs can be assessed as severe. An event will be defined as serious when it meets one of the criteria described in Protocol Section 9.1.3.

7.3.2 Relatedness (Causality) to Study Drug

The assessment of causality will be based on the information available and may be changed upon receipt of additional information.

Causality should be assessed using the following categories:

- Unrelated/Unlikely Related: clinical event with an incompatible time relationship to investigational agent administration, and that could be explained by underlying disease or other drugs or chemicals or is incontrovertibly not related to the investigational agent
- Possibly related: clinical event with a reasonable time relationship to investigational agent administration, and that is unlikely to be attributed to concurrent disease or other drugs or chemicals
- Probably related: clinical event with plausible time relationship to investigational agent administration, and that cannot be explained by concurrent disease or other drugs or chemicals

7.4 Pregnancy

Pregnancy itself is not regarded as an AE unless there is a suspicion that the investigational product (IP) may have interfered with the effectiveness of a contraceptive medication. Pregnancy in a patient's partner is not considered an AE. Congenital abnormalities/birth defects and spontaneous miscarriages should be reported and handled as SAEs. Elective abortions without complications should not be handled as AEs. The outcome of a pregnancy will be followed-up and documented even if the patient was withdrawn from the study. See Protocol Section 9.6.4 for further information on reporting of pregnancy.

An induced elective abortion to terminate a pregnancy without medical reason is not regarded as an AE. However, an induced therapeutic abortion to terminate a pregnancy because of complications or medical reasons must be reported as an SAE. The underlying medical diagnosis

for this procedure should be reported as the SAE term. A spontaneous abortion in a study patient is always considered an SAE.

7.5 Overdose

Any instance of overdose (suspected or confirmed and irrespective of whether or not it involved study drug must be communicated to the Sponsor or a specified designee within 24 hours and be fully documented as an SAE. Details of any signs or symptoms and their management should be recorded including details of any antidote(s) administered.

An overdose of study drug is not expected to occur in this study, as a single dose is being administered intranasally. Should patients receive a higher dose than the allocated dose, this should be reported in the eCRF and the Sponsor should be informed. Any deviations from the assigned dose will be handled as a protocol deviation.

7.6 Procedures for Recording and Reporting Adverse Events

7.6.1 *Recording Adverse Events*

To improve the quality and precision of AE data, Investigators should observe the following guidelines:

- Whenever possible, use recognized medical terms when recording AEs on the AE page of the eCRF. Do not use colloquialisms, jargon, or abbreviations.
 - If known, record the diagnosis (ie, disease or syndrome) rather than component signs and symptoms on AE pages of the eCRF (eg, record “congestive heart failure” rather than “dyspnea”, “rales”, and “cyanosis”). However, signs and symptoms that are considered unrelated to an encountered syndrome or disease should be recorded as individual AEs on the eCRF page. For example, if congestive heart failure and severe headache are observed at the same time, each event should be recorded as an individual AE.
 - Adverse events occurring secondary to other events (ie, sequelae) should be identified by the primary cause. A primary AE, if clearly identifiable, generally represents the most accurate clinical term to record on the AE page of the eCRF. If a primary SAE is recorded on an AE eCRF page, events occurring secondary to the primary event should be described in the narrative description of the event.
 - Any laboratory abnormalities that are identified by the Investigator as clinically significant, as applicable, are to be considered AEs and recorded on the AE eCRF page.
-

7.6.2 Special Reporting Situations

Hospitalization or Death

Hospitalization and death are outcomes of an event. The event that resulted in hospitalization or death should be recorded and reported on the SAE form and the AE eCRF page.

As noted in Protocol Section 9.2 and Section 8.2.6, hospitalizations and deaths related to worsening fever, cough, shortness of breath, resting SpO₂ or resting pulse rate or symptoms of COVID-19 at Screening will not be considered SAE, although narratives of the hospitalizations and causes of death will be reported to and reviewed by the DMC in real time.

Surgical or Diagnostic Procedures

The illness leading to a surgical or diagnostic procedure is to be recorded as an AE/SAE, not the procedure itself. The procedure is to be captured in the case narrative as part of the action taken in response to the illness.

8 QUALITY CONTROL AND QUALITY ASSURANCE METHODS FOR DATA ANALYSIS

9 STATISTICAL METHODS

9.1 General

The statistical analysis will be conducted following the principles specified in the International Council for Harmonisation (ICH) Topic E9 Statistical Principles for Clinical Trials (CPMP/ICH/363/96).

Baseline is defined as data collected closest to randomization prior to any study drug dosing. For resting SpO₂ and resting pulse rate, Baseline is defined as the average of the two measurements at Screening. All analyses and summary statistics will be presented by treatment group (NasoVAX, placebo) across cohorts, as well as by treatment group pooled across all cohorts, for each analysis set separately.

All statistical tabulations and analyses will be done using the SAS Version 9.4 or higher. Unless otherwise noted, continuous variables will be presented by summary statistics (eg, mean, standard deviation [SD], median, minimum, and maximum). The continuous efficacy endpoints

will be presented by means and 95% confidence intervals (CIs). Categorical variables will be presented by frequency counts and percentages. The categorical endpoints will be by frequency distributions (percentages and 95% CIs calculated according to Clopper-Pearson method). The study is considered exploratory, and inferential statistics will be employed as appropriate across cohorts, as well as by treatment group pooled across all cohorts.

Most of the 95% CIs will be produced using standard methods, but in some instances the Clopper-Pearson method will be used, and in these latter situations the method will be footnoted.

In the data listings, for each patient the time point will be presented as study day defined relative to the first dose of investigational product. Study day will be calculated as: event date – first date +1 (when event date \geq first dose date), and as event date – first date (when event date is prior to date of first investigational product). The day of first investigational product intake is Day 1, the day prior to first investigational product intake is Day -1, there is no Day 0.

Unless otherwise specified, baseline will be the last available measurement prior to the first dose of investigational product.

For all summary tables, the values from unscheduled visits will not be considered and the repeated values will only be used if the preceding value was hemolyzed or if the specimen was lost or the quantity was insufficient to run the assay. However, in individual data listings, both repeated measurements and those from unscheduled visits will be included.

All investigational product dosing will be listed and summarized by cohorts.

9.2 Multicenter Studies

This is a multi-center study which makes use of up to 6 clinical sites in the United States.

9.3 Examination of Subgroups

No subgroup analyses are planned.

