9.9 Analysis of Efficacy Data

Efficacy analyses will be conducted using the mITT and PP Populations with the primary conclusions drawn from the mITT Population. Placebo will be the collective (pooled) across cohorts.

Descriptive statistics will be used to evaluate differences between Baseline and post-Baseline efficacy endpoints. The study is considered exploratory, and inferential statistics will be employed as appropriate.

For the purpose of study efficacy endpoints, resting SpO₂ and resting pulse rate will be assessed on observed data only; if data is missing, it will not be imputed.

The p-values from significance tests will be obtained at a one-sided significance level of 0.025.

No multiplicity adjustments will be made for the efficacy endpoints.

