9.9.3 Analysis of Time to Event Data Endpoints

Time to event data endpoints – the primary endpoint of the first 4.0% decrease or greater from Baseline in resting SpO₂ on two consecutive measurements during the 14 days of home follow-

up, or hospitalization; the secondary endpoints of the first incidence of resting pulse rate ≥ 125 beats per minute during the 14 days of home follow-up, or hospitalization; and all-cause mortality through Day 42 – will be analyzed by the Kaplan-Meier method. The summary statistics will be tabulated by treatment arms over visits and will include number of patients without event, number patients censored, 25th, 50th, and 75th percentiles with 95% CIs, the event rates across all visits with 95% CIs. Kaplan-Meier estimates are calculated with the PROC LIFETEST procedure in SAS. The CIs of the event rates will be calculated via log-log transformation method (default option CONFTYPE=LOGLOG in SAS) based on standard errors computed using the Greenwood's formula. Time to event data comparisons will be made by treatment group and may include comparisons for cohort or stratification factors (ages 35-64 years vs. ages 65 years and above, one or more risk factors present vs. no risk factors present). The summary statistics may also have the p-values from log-rank test to compare changes in events between NasoVAX cohorts and pooled placebo and overall NasoVAX and pooled placebo groups. The log-rank test stratified by age groups and risk factors will also be performed. The Kaplan-Meier curves will also be plotted for each NasoVAX cohort and pooled placebo groups.

Non-informative censoring is assumed, as censored patients the same probability of experiencing an event as patients that remain in the study. Patients who do not meet the event or loss to follow-up before the study-end are censored at the last day during the 14 days of home follow-up or hospitalization in resting SpO₂ and resting pulse or at Day 42 for all-cause mortality.

9.9.4 *Analysis for Covariates*

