9.10 Analysis of Safety Data

Quantitative safety data, including the frequencies of AEs, oral temperatures, use of antipyretics and bronchodilators, and length of hospital and ICU stay, will be summarized using descriptive statistics and frequency distributions. Qualitative safety data will be summarized by frequencies and percentages. All summaries will be presented by overall NasoVAX, NasoVAX cohort, and pooled placebo groups. AEs will be coded using the latest version of MedDRA, and severity will be coded using the latest version of the CTCAE, v.4.0.3. Concomitant medications will be coded using the latest version of the World Health Organization (WHO) drug dictionary. Safety comparisons will be made by treatment group and include comparisons for cohort or stratification factors (ages 35-64 years vs. ages 65 years and above, one or more risk factors present vs. no risk factors present).

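### SAP 9.3 rules out subgroup analyses, but 9.9.1 to 9.9.3 and 9.10 plan or allow them by cohort, age group and risk factor, with no multiplicity control, no interaction estimate and a pooled placebo comparator

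*SAP*

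**What the plan says.** SAP 9.3 consists of one sentence: "No subgroup analyses are planned". Other sections of the SAP provide for comparisons within parts of the population.

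- **9.9.1 (primary endpoint and hospitalization by oxygen level).** Each NasoVAX group is to be compared with pooled placebo by Fisher's exact test. Score intervals for the difference and a CMH test are also planned for NasoVAX cohorts against pooled placebo. The wording is firm.
- **9.9.2 (SpO₂ and pulse rate).** P-values from a t-test or Mann-Whitney test are planned for each NasoVAX cohort against pooled placebo, and for NasoVAX overall.
- **9.9.3 (time to event).** "Time to event data comparisons will be made by treatment group and may include comparisons for cohort or stratification factors", with the levels given as "ages 35-64 years vs. ages 65 years and above, one or more risk factors present vs. no risk factors present". The summaries may also carry "p-values from log-rank test to compare changes in events between NasoVAX cohorts and pooled placebo".
- **9.10 (safety).** "Safety comparisons will be made by treatment group and include comparisons for cohort or stratification factors". This paragraph names no test.

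For efficacy, 9.9 sets the rule for every test: "The p-values from significance tests will be obtained at a one-sided significance level of 0.025". It adds: "No multiplicity adjustments will be made for the efficacy endpoints". The only treatment interaction in the SAP's models is treatment-by-visit, in the MMRM of 9.9.2.

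**The concern.** Section 9.3 and the later sections cannot all stand. A reader of 9.3 would take any cohort or stratum result in the study report as unplanned. A reader of 9.9.1 would take the cohort tests as planned.

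Three safeguards are missing.

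- The time-to-event comparisons by age and risk factor are optional, so the choice to make and report them can be taken after the data are seen.
- No order of testing or error control covers the levels.
- Nothing estimates whether the treatment effect differs between levels. The stratified CMH and log-rank tests adjust for age and risk; they do not test interaction. A small p-value in one level does not show that the effect is larger there.

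The cohort comparisons have a separate weakness. The comparator is placebo pooled over three cohorts that were deliberately enrolled at increasing risk, so a low-risk NasoVAX cohort is compared with a placebo group at higher average risk.

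At stake is the reading of an isolated favourable result, for example in Cohort 1 or in patients aged 65 and above, from a study of about 96 patients.

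**Working it through.** **Inputs from the documents.** One-sided level 0.025 per efficacy test (SAP 9.9). Cohorts of about 20, 28 and 48 patients, 1:1, so 10, 14 and 24 per arm, 48 per arm in total (SAP 4.1, Table 1). Two age levels, two risk levels and three cohorts (SAP 9.9.3). The documents give no event rates and no sample-size derivation (SAP 9.4).

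**Assumed.** Cell sizes: Cohort 1, 20; Cohort 2, 20 under 65 and 8 aged 65 or over; Cohort 3, 12/16/8/12 by age and risk factor. This gives 68 patients under 65 and 28 aged 65 or over, and 68 without and 28 with a risk factor. Event rates are assumed as shown below.

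**Step 1: the plan's own figure.** One test at its stated level has a 2.5% false-positive chance. That level is set, not derived.

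**Step 2: several tests, each at its full nominal level, no drug effect.** For k independent tests the chance of at least one false benefit is 1 − 0.975^k. Three separate cohorts give 1 − 0.975³ = 7.3%. Seven independent tests would give 1 − 0.975⁷ = 16.2%, but the seven levels overlap, so this is only an upper bound. Simulating correlated normal statistics for the overlapping levels, each cohort against its own placebo:

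| Family of tests | Chance of at least one false benefit |
|---|---|
| Four age and risk strata | 8.0-8.2% |
| Four strata plus overall test | 8.4-8.6% |
| Four strata plus overall test and three cohorts | 12.4-12.5% |

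Other assumed age and risk mixes give 11.9-12.7% for the seven levels without the overall test.

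**Step 3: the same families with actual event counts.** In small strata with few events, tests do not reach 2.5%. Equal event rates of 5-30% were assumed, with a binary score test standing in for log-rank:

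| Family of tests | Score test | Fisher's exact test |
|---|---|---|
| Four age and risk strata | about 3-8% | 0.3-4.0% |
| Four strata, overall test and cohorts | about 5-12% | 0.6-6.0% |

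The low end is at a 5% event rate and the high end at 30%.

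**Step 4: the comparator the SAP actually uses for cohorts.** Suppose there is no drug effect and the event risk by cohort is 10%, 20% and 40% (assumed). The expected pooled placebo rate is (10 × 0.10 + 14 × 0.20 + 24 × 0.40)/48 = 13.4/48 = 27.9%. NasoVAX Cohort 1 has an expected rate of 10%, so it appears about 18 points better with no effect. With risks of 15%, 20% and 25%, the pooled rate is (1.5 + 2.8 + 6.0)/48 = 10.3/48 = 21.5%, a gap of 6.5 points. Simulated chance of a false benefit against pooled placebo:

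| Assumed risk by cohort | Any cohort, Fisher | Any cohort, log-rank | Cohort 1 alone, Fisher / log-rank |
|---|---|---|---|
| 10/20/40% | 8.2% | 12.4% | 5.2% / 8.2% |
| 15/20/25% | 1.7% | 2.8% | 0.4% / 0.7% |
| 20/20/20% | 1.7% | 3.0% | 0.1% / 0.2% |

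A steep risk gradient therefore matters more than the number of cohort tests; with a mild gradient little happens. These figures are for unstratified tests. The stratified CMH and log-rank tests would remove part of the imbalance by matching on age group and risk factor.

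**The case against.** The strongest reply is that this is an exploratory study whose SAP says openly that no multiplicity adjustment is made. The protocol's primary analysis (10.3.2) is one overall CMH test stratified by age and risk factor, and protocol 10.4 says the primary analysis stays the same whatever the SAP adds. Results by cohort follow from the sequential design and are foreseen in protocol 10.3.1. All of this stands, and it keeps the point moderate.

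Two stronger readings are tempting, and the documents do not support them.

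- *The plan multiplies the 2.5% error rate by a fixed factor of three or five.* This needs a p-value in every level and every test at its full nominal level. SAP 9.9.3 names no test within an age or risk level: its log-rank p-values are for NasoVAX cohorts and NasoVAX overall against pooled placebo, and age and risk enter through a stratified test. The 9.10 paragraph is about safety, names no test and cannot add an efficacy finding at 0.025. (SAP 9.10.2 does name a Kruskal-Wallis test by cohort, but for diary symptoms.) Event rates are not given, and at low rates the inflation largely disappears, above all with Fisher's test.
- *The SAP permits an efficacy claim from one favourable stratum.* No passage says so. The SAP simply does not exclude it.

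It can also be said that an interaction test in about 96 patients has little value. That is fair for a test, which is why an estimate with its interval is preferable.

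The contradiction between the sections, the optional wording and the pooled comparator remain after these replies.

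**Conclusion.** The contradiction is certain and needs no assumption: 9.3 excludes what 9.9.1 and 9.9.2 plan, 9.9.3 allows and 9.10 plans for safety. The absence of a treatment-by-factor interaction and of any error control over the levels is equally clear.

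The numerical consequence is conditional. The figures of about 8% and about 12% are ceilings for the assumed cell sizes, with each cohort against its own placebo and full nominal levels; the ranges in step 3 are the more realistic guide. They concern one endpoint, while 9.9.3 lists three. The pooled placebo can produce a false cohort benefit by itself, but its size depends wholly on how steeply risk rises from Cohort 1 to Cohort 3, which the documents do not state.

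This is a moderate point. It should be corrected before unblinding and does not undermine the protocol's overall primary comparison.

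**What to change.** Replace SAP 9.3 with text to this effect: results by cohort, age group and risk factor are exploratory. For every level of each factor, NasoVAX is compared with concurrent placebo in the same level, shown as estimates with 95% CIs and without within-level p-values. For the primary endpoint, one treatment-by-factor interaction estimate with its CI is reported per factor. No efficacy conclusion rests on a single level.

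Then align the other sections:

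- **9.9.1 and 9.9.2:** remove the per-cohort tests against pooled placebo and refer to 9.3. Word the CMH test as the overall NasoVAX against placebo comparison, stratified by age group and risk factor, and keep it as the primary analysis.
- **9.9.3:** replace the optional wording on cohort and strata, and the cohort log-rank p-values against pooled placebo, with a reference to 9.3.
- **9.10:** refer to 9.3 for the safety breakdown, and state that it is descriptive.

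The age levels should be those used at randomization: the SAP gives 35-64 years where the current protocol gives 18-64.

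The cost is SAP wording, a forest plot and a few interaction models. Within-level p-values are given up, and the interaction estimates will be imprecise with about 96 patients.

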9.4 Sample Size

The study is considered exploratory to assess the initial safety of NasoVAX in COVID-19 and response to treatment. The sample size chosen for this study was considered adequate to meet the study objectives and was selected without statistical significance considerations.

9.5 Analysis Populations

Consented Population: All patients who signed the informed consent.

Randomized Population: All patients who were randomized to receive any study medication.

Safety Analysis Set: All patients who receive any study drug. Patients will be analyzed according to the treatment that they receive.

Modified Intent-to-Treat (mITT) Analysis Set: All randomized patients who receive any amount of study drug, have a Baseline and at least one post-Baseline resting SpO₂ measurement. Patients will be analyzed according to the treatment that they receive. Patients will be analyzed according to the treatment that they receive. This analysis set will be used for primary and secondary analyses.

Per Protocol (PP) Set: All randomized patients who receive any amount of study drug according to the correct treatment assignment and who have 80% of twice daily results from resting SpO₂ measurements through Day 14 or hospitalization.

All important protocol deviations documented during study will be collected and finally assessed as major or minor protocol deviation after data base lock and prior to unblinding.

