### **3 STUDY ENDPOINTS**

#### **3.1 Primary Efficacy Endpoint**

The primary endpoint is the proportion of patients with clinical worsening, defined as an absolute 4.0% decrease from Baseline in resting SpO2 on two consecutive measurements during home follow-up, or hospitalization.

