### 10.2 Analysis Sets

**Safety Analysis Set:** All patients who receive any study drug. Patients will be analyzed according to the treatment that they receive.

**Modified intent to treat (ITT) Analysis Set:** All randomized patients who receive any amount of study drug, have a Baseline and at least one post-Baseline resting SpO2 measurement. Patients will be analyzed according to the treatment that they receive. Patients will be analyzed according to the treatment that they receive. This analysis set will be used for primary and secondary analyses.

**Per Protocol (PP) Set:** All randomized patients who receive any amount of study drug according to the correct treatment assignment and who have 80% of twice daily results from resting SpO2 measurements through Day 14 or hospitalization.

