3.2 Secondary Efficacy Endpoints

Secondary efficacy endpoints are:

1. Maximal severity of COVID-19 after treatment, as assessed by the following:
 - average decrease in resting SpO₂ from Baseline resting SpO₂ at Screening during the 14 days of home follow-up or hospitalization
 - average increase in resting pulse rate from Baseline resting pulse rate at Screening during the 14 days of home follow-up or hospitalization
 - proportion of patients requiring hospitalization through Day 42 according to maximal level of oxygen supplementation:
 - No oxygen supplementation
 - Oxygen supplementation with nasal cannulae
 - Oxygen supplementation with high flow device or non-invasive ventilation
 - Mechanical ventilation
2. All-cause mortality through Day 42

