After discharge on Day 1, patients will return home for the duration of the study. Patients are to measure resting SpO₂, resting pulse rate, and oral temperature twice daily at 09:00 hours and 16:00 hours, with a 1-hour window around each time point, and at any time they experience worsening symptoms until Day 14 or hospitalization, whichever comes first. Patients are to record COVID-19-related symptoms daily during this same time period. Study center personnel will contact patients daily by telephone during this period to document the patient's clinical status, record concomitant medications and monitor for AEs.

After Day 14, study center personnel will contact patients via telephone approximately every 7±2 days for 14 additional days to determine if they were hospitalized and to follow AEs that were not resolved by Day 14. If the patient is hospitalized at any time, the dates and times of hospital admission/discharge, ICU admission/discharge, and ventilation requirement are to be recorded, as applicable. Patients who remain hospitalized at the end of 28 days will be followed through Day 42 or death, whichever is sooner.

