6.2.5 Additional Data Collection in Hospitalized Patients

Additional data to be collected for patients hospitalized due to COVID-19 through Day 42 to include the following:

- Date and time of hospital admission and discharge
- If transferred to ICU, date and time of ICU admission and discharge
- Requirement for oxygen (yes/no), and if yes, method of oxygenation (mask/nasal prongs, non-invasive ventilation, or high-flow oxygen; intubation and mechanical ventilation
 - If required ventilation, start date and time of ventilation, method of ventilation including whether intubated (yes/no)
- Change in ambulatory status
- Death

It is anticipated that most of this information will be obtained from the medical record. When necessary, a family member, designated legal representative or caregiver, as permitted by informed consent, will be contacted if the patient has expired or is too ill or otherwise unable to provide this information.

The rate (liters/min) of oxygen administered is to be captured as a concomitant medication. If, in the Investigator's opinion, a patient required a higher level of oxygenation, but did not receive due to resource availability, this should be documented.

Furthermore, if, in the Investigator's opinion, the patient required a higher level of care (ie, admittance to the ICU) but did not receive due to resource availability, this should be documented.

6.2.6 *Vital Status*

Vital status is to be documented at each study contact. If the patient died due to a reason other than COVID-19, the primary cause of death is to be recorded and reported as an SAE. Death due to worsening fever, cough, shortness of breath, resting SpO₂ or resting pulse rate or COVID-19 symptoms that are reported at Screening (Protocol Section 8.1.2) is not considered to be an SAE in the context of this study although cause of death will be reviewed by the DMC in real time.

6.3 **Safety Assessments**

6.3.1 *Height, Weight and Body Mass Index (BMI)*

Height (cm) and weight (kg) will be measured and recorded at Screening. BMI will be subsequently be calculated from these measurements.

6.3.2 *Physical Examination*

A cardiovascular and respiratory-focused physical examination will be performed by trained medical personnel during Screening.

6.3.3 *Screening Vital Signs*

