9.7 Subject Accountability

The screening outcomes will be listed and summarized based on the Consented Population. Consented population in the study will be included in the summary of pre-randomized patient status. The summary will include all patients consented, patients who completed screening, and patients who were screening failure. The reasons for screening failure will also be summarized.

Summaries of analysis populations and patient disposition will be presented by NasoVAX cohort, all NasoVAX cohorts combined, placebo pooled from all cohorts, and overall (all NasoVAX cohorts and pooled placebo) based on the Safety Population and will contain the following information:

- Number of patients who were randomized
- Number and percentage of patients who were dosed (Safety Population)
- Number and percentage of patients who did not receive all doses
- Number and percentage of patients in safety population who completed the study
- Number and percentage of patients who discontinued early and reason for early discontinuation of study

The number and percent of patients in each analysis population will also be tabulated.

A listing will present dates of completion or early withdrawal and the reason for early discontinuation of investigational product treatment and discontinuation of study, respectively, if applicable, for each patient.

The randomization allocation and exclusion from each population will also be listed.

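### The primary efficacy set requires a post-Baseline SpO2 reading, so a dosed patient hospitalized without one has a primary-endpoint event but is left out of the primary analysis

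*SAP*

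**What the plan says.** **The set.** SAP 9.5 admits to mITT only randomized patients who "receive any amount of study drug, have a Baseline and at least one post-Baseline resting" SpO2 measurement. Protocol 10.2 has the same condition and adds: "Patients will be analyzed according to the treatment that they receive. This analysis set will be used for primary and secondary analyses". SAP 9.9 plans efficacy analyses on mITT and PP only, "with the primary conclusions drawn from the mITT Population".

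**The endpoint.** Under Protocol 3.1, clinical worsening is a 4.0% fall in resting SpO2 "on two consecutive measurements during home follow-up, or hospitalization". SAP 3.1 and 9.9.1 agree. The hospitalization component needs no SpO2 value.

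**Data collection.** Patients measure SpO2 twice daily and "at any time they experience worsening symptoms until Day 14 or hospitalization, whichever comes first" (SAP 4.1). Hospitalization is found by telephone, from family or caregivers where needed, and from the medical record (SAP 4.1, 6.2.3, 6.2.5). SAP 6.2.5 introduces the hospital data with "Additional data to be collected for patients hospitalized due to COVID-19 through Day 42 to include the following"; the list covers admission, ICU, oxygen method, ventilation, ambulatory status and death, and does not name SpO2.

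**Other endpoints on the same set.** SAP 3.2 includes hospitalization by maximal oxygen support and "All-cause mortality through Day 42". Neither depends on a home reading.

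**The concern.** Membership of the primary set depends on a measurement made after randomization, and the outcome can prevent that measurement. There are two routes. A patient may be admitted before the first reading. Or a patient may never record one and be admitted later; this route is not confined to the first hours. In both, a known primary event leaves the numerator and the patient leaves the denominator.

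If such losses fall more on NasoVAX, the drug looks better than it is; if more on placebo, worse. Equal losses change little. The same patients drop out of the secondary hospitalization and mortality analyses, although those outcomes are recorded for them.

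**Working it through.** **Step 1. Does any provision keep the patient in?**

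- The missing-data text (SAP 9.9.6) allows LOCF or multiple imputation as an option in sensitivity analyses. It does not change who belongs to mITT.
- The PP set asks for 80% of twice-daily SpO2 results, so it does not clearly recover a patient with none.
- The Safety Analysis Set keeps every dosed patient, but no efficacy analysis is planned on it.
- SAP 9.7 tabulates the sets and states: "The randomization allocation and exclusion from each population will also be listed". This shows the loss but does not correct the result.

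No provision restores the patient.

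**Step 2. How long is the gap before the first scheduled reading?** If the visit is after 16:00, home readings start the next morning (SAP 6.2.1.2; Table 2, footnote d). The 09:00 reading has a 1-hour window, so the longest gap is 16:00 on Day 1 to 10:00 on Day 2: 8 + 10 = 18 hours.

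**Step 3. How many patients?** The documents give no rate. Let q be the assumed share of the 96 dosed patients who are hospitalized with no post-Baseline reading. Expected number lost = 96q; chance of losing at least one = 1 − (1 − q)^96.

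| q (assumed) | Expected lost | Chance of at least one |
|---|---|---|
| 0.5% | 0.5 | 38% |
| 1% | 1.0 | 62% |
| 2% | 1.9 | 86% |
| 5% | 4.8 | 99% |

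**Step 4. Effect of one lost event on an arm of 48.** With x events, the proportion falls by x/48 − (x − 1)/47 = (48 − x)/(48 × 47). For x = 4 this is 44/2256 = 1.95 points; for x = 10 it is 38/2256 = 1.68 points. Both are about 2 points.

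**Step 5. Illustration on the test.** Event counts are assumptions. The p values are one-sided, from an unstratified Mantel-Haenszel (MH) test without continuity correction and from Fisher's exact test.

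| NasoVAX v placebo | Difference (points) | MH | Fisher |
|---|---|---|---|
| 4/48 v 10/48 (nobody lost) | −12.5 | 0.042 | 0.073 |
| 3/47 v 10/48 (one NasoVAX event lost) | −14.5 | 0.021 | 0.038 |
| 4/48 v 9/47 (one placebo event lost) | −10.8 | 0.064 | 0.108 |
| 3/47 v 9/47 (one lost in each arm) | −12.8 | 0.033 | 0.060 |

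Starting from 6/48 v 10/48 (0.138 / 0.206), losing one, two or three NasoVAX events gives 0.088 / 0.140, 0.050 / 0.086 and 0.0251 / 0.046. Neither test falls below 0.025.

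The strata in the plan are age and risk group, whose sizes are not given. As a substitute I stratified by cohort, assuming 0, 1 and 3 NasoVAX events against 1, 3 and 6 placebo events in Cohorts 1 to 3. The MH p value of 0.042 becomes 0.021 if a Cohort 3 NasoVAX event is lost, or 0.020 if a Cohort 2 event is lost.

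**Step 6. Average effect if both arms lose the same share.** Each arm's proportion p becomes (p − q)/(1 − q), so the expected difference d becomes d/(1 − q). With d = −12.5 points this is −12.5/0.995 = −12.6 at q = 0.5% and −12.5/0.98 = −12.8 at q = 2%. In simulation with true rates of 8.3% and 20.8% and q = 1%, the MH result at 0.025 changed in about 8% of trials. With equal event rates of 10% or 20% it changed in about 1%, and the false-positive rate stayed at or below 0.025.

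**The case against.** The strongest reply is that the problem is rare and mostly visible. The first reading is due within 18 hours, patients also measure when symptoms worsen, and exclusion criterion 3 removes those expected to be admitted within 24 to 48 hours. Hospital stay is a safety endpoint on all dosed patients, the stopping rules count hospitalizations by arm and cohort without reference to mITT, and exclusions are listed. All of this stands, and it keeps the point modest. It does not put the event back into the primary result.

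The trial is exploratory, and its size was set without significance considerations (SAP 9.4). That stands too. A reader might infer from Step 5 that one patient would decide the trial. The documents do not support that: the MH crossing needs a start just above 0.025 and a loss on NasoVAX only, and Fisher's test crosses in none of these examples. The pooled 48 v 48 contrast is also only one of those planned, since SAP 9.9.1 compares NasoVAX cohorts with pooled placebo.

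A reader might also infer that no SpO2 value can exist after admission. That is too firm. SAP 3.2 describes the average SpO2 decrease over home follow-up or hospitalization, and the hospital list need not be exhaustive. What can be said is that SpO2 is not among the listed items and that the documents do not clearly say whether a hospital value would qualify a patient for mITT.

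**Conclusion.** The gap in the definition is certain on the text: a stated rule removes known primary events on a post-randomization condition. Its practical size is probably small: about 2 points in an arm of 48 per lost event, in either direction, and little average distortion if both arms lose the same share. The share affected and all event counts are assumptions; the documents give neither.

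A reader might go further and conclude that death must join the primary composite. The documents do not require this: mortality is a separate secondary endpoint, and adding it would change the primary endpoint rather than repair the set. At most it is a sensitivity analysis.

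The point should be fixed, because the correction is simple and uses data already collected.

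**What to change.** Before unblinding, amend Protocol 10.2 together with SAP 9.5 and 9.9. Protocol 10.4 says the primary analysis stays the same, so the SAP alone should not change it.

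1. Define the primary efficacy set as all randomized patients who received study drug, analyzed as randomized, with no post-Baseline SpO2 requirement. Count hospitalization as an event whether or not a reading exists.
2. Keep the current mITT as a sensitivity set. Report by arm how many patients it excludes and how many of those were hospitalized or died.
3. If the sponsor keeps the current primary set, pre-specify the analysis of all dosed patients as a sensitivity analysis.

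**Cost.** No new data are needed, but the protocol change needs written IRB approval (Protocol 12.5). Patients with no reading and no known admission, including early withdrawals, would be scored as non-events. That is in effect an imputation and sits uneasily with the observed-data-only rule in SAP 9.9, so the SAP should acknowledge it and their number should be reported by arm.
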